6.6. PHYSICAL EXAMINATION

Any physical examination abnormality considered clinically significant in the medical and scientific judgment of the Investigator (i.e., not related to progression of underlying disease), will be reported as an AE.

6.7. EYE EXAMINATIONS

Eye examination data will be performed during the study by an appropriately qualified professional. Any abnormality considered clinically significant, will be reported as an AE.

Best corrected visual acuity (BCVA) can be assessed using the LogMAR scale, ETDRS letters or Snellen line. All results will be converted to the LogMAR scale before calculating changes from baseline at each visit for left and right eye BCVA (Roy 2003).

Where the Snellen scale has data recorded as x/y the MAR value is calculated by dividing y by x and then the LogMAR is the base 10 logarithm of the MAR value [i.e., $\text{LogMAR} = \log_{10}(\text{MAR})$]. Hence, higher scores indicate worse BCVA and increases from baseline indicate deterioration.

A change of 0.02 in LogMAR is equivalent to 1 letter. Hence, a Snellen scores with ‘-z’ or ‘+z’ indicating z letters fewer, or z letters more, respectively, will require an adjustment to the LogMAR score; 0.02 will be added or subtracted, respectively, for each letter (z).

e.g.,

$$20/15-1: \text{LogMAR} = \text{Log}_{10}(15 \text{ divided by } 20) + 0.02 = -0.105$$

$$20/15+1: \text{LogMAR} = \text{Log}_{10}(15 \text{ divided by } 20) - 0.02 = -0.145$$

If the Snellen scale is not reported in x/y format or x/y±z format, then the conversion to logMAR will not be done.

A change of 0.3 LogMAR (equivalent to 15 letters or 3-line change) is considered meaningful.

Refraction error based on spherical equivalent will be derived for each eye using the following formula:

$$\text{Spherical Equivalent (diopters)} = \text{cylinder (diopters)}/2 + \text{sphere (diopters)}$$

Changes from baseline at each visit will be calculated. A change ≥ 0.75 diopters will be reported as an AESI.

Cataract are classified and graded against the Lens Opacity Classification System III (LOCS III) for nuclear opalescence, nuclear colour, cortical and posterior subcapsular cataracts. A change was made to the grading system used during the study. The original system was used at the screening visit for 30 subjects who were subsequently randomized. As the original data cannot be converted to the revised LOCS III grading system the data for these subjects (screening results recorded in the original format, and Week 12 and Week 24 results recorded in the new format) will only be listed and medically reviewed to identify any possible development of cataracts. Changes from baseline will be calculated for all other subjects. Higher scores equate to a deterioration in cataracts. The largest increase from baseline (or smallest decrease if both eyes show a reduction from baseline) across the eyes will be identified at each visit.

6.8. COVID-19 EXPOSURE AND VACCINATION DATA

Information on whether a subject has had exposure to COVID-19 or received a COVID-19 vaccination is collected on a specific eCRF page. Further details of COVID-19 events will be recorded in either medical history or on an adverse event page, depending on the timing; and further details of COVID-19 vaccinations will be recorded on the concomitant page.

7. ANALYSIS SETS AND PROTOCOL DEVIATIONS

7.1. SCREENED ANALYSIS SET

The screened analysis set will include all subjects who signed the informed consent form and are screened for participation in this study. This analysis set will only be used for the purposes of describing subject disposition.

7.2. RANDOMIZED ANALYSIS SET

The randomized analysis set will include all randomized subjects. This analysis set will only be used for the purposes of describing subject disposition.

7.3. SAFETY ANALYSIS SET

The safety set will include all subjects who signed the informed consent form, completed screening and received at least one dose of study drug. The safety analysis set summaries will be based on the actual treatment received. The safety analysis set will be used for all baseline and safety analyses.

7.4. FULL ANALYSIS SET

The full analysis set (FAS) will include all subjects in the randomized set who received at least one dose of study drug and have not been subsequently discontinued from the study for failing eligibility criteria. Subjects will be analysed according to the treatment they were assigned at randomization. The FAS will be used for baseline analyses and will be the primary analysis set for efficacy.

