3.5 Termination or Suspension of Investigational Sites

A study site may be terminated prematurely or suspended if the site (including the Investigator) is found to be in significant violation of GCP, the protocol, or the contractual agreement, or is unable to ensure adequate performance of the study, or for reasons as otherwise permitted by the contractual agreement.

3.6 Conditions for Individual Subject Discontinuation of Study Drug or Withdrawal from the Study

[figure not shown]
The primary reason for permanent discontinuation of a subject from the study drug should be recorded in the electronic Case Report Form (eCRF). Individual subjects may be discontinued from the study drug in the following circumstances:

1. Concurrent enrolment in other clinical studies involving investigational products or enrolment in other types of clinical research judged not to be scientifically or medically compatible with this study.
2. Use of a prohibited concomitant medication.
3. Major protocol deviation e.g., the discovery after administration of the first dose of study medication that the subject failed to meet protocol entry criteria or did not adhere to protocol requirements, and continued participation poses an unacceptable risk to the subject’s health or undermines the ability to achieve the objectives of the study.

4. Lost to follow-up. The subject did not return to the study center and attempts to contact the subject were unsuccessful. Attempts to contact the subject must be documented.
5. Evidence of pregnancy during the treatment period of the study.
6. Clinically significant changes from baseline in ECG recordings considered treatment-related including an increase from baseline in heart rate corrected QT interval using Fridericia's formula (QTcF) to a value of ≥ 500 millisecond (msec). Single ECGs should be repeated at 5-minute intervals, 3 times, to confirm any increased QTcF interval values. In the event of an increased QTcF interval of ≥ 500 msec, the subject must be monitored until the value returns to below 500 msec.
7. Clinically significant muscle injury including test abnormalities (e.g., CK) as defined in [Section 3.7.1](#).
8. Clinically significant liver toxicity including test abnormalities (e.g., ALT/AST) as defined in [Section 3.7.2](#).
9. Clinically significant kidney toxicity including test abnormalities (e.g., creatinine levels) as defined in [Section 3.7.3](#).

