6.9 Subject Continuation In Study Off IMP

If a subject discontinues taking study drug, they will be strongly encouraged to continue in the study for their Week 12 and Week 24 visits (see [Figure 3](#)). If they agree to remain in the study off-IMP as a minimum they will be requested to complete the following assessments:

- Review concomitant medications and non-drug treatments
- Review of adverse events

- Vital signs (including temperature)
- MFIS
- 12MWT

Table 2: Schedule of Activities

Time and Events Table	Screening	Baseline ^{1, 2} (Day 1)	Week 2 ³ (Day 14)	Week 4 ³ (Day 28)	Week 8 (Day 56)	Week 12 ^{2, 4} (Day 84)	Week 16 (Day 112)	Week 18 ³ (Day 126)	Week 20 (Day 140)	Week 24 ^{2, 4} (Day 168).	Early Term ^{2, 5}	Follow Up ³ (21-28 days post last dose)
Visit number	1	2	3	4		5		6		7		8
Window (days)			±3	±3		±7		±7		±7		
Informed Consent	X											
Completion of Proforma and data entered into eCRF ⁶	X											
Demographics	X											
Medical/medication/drug/alcohol/tobacco history ⁷	X											
Physician completion of PMM phenotypic description		X								X	X	
Physical exam ⁸	X	X				X				X	X	
12-lead ECG	X	X				X				X	X	
Supine Vital signs (BP, PR and temperature)	X	X	X	X		X		X		X	X	X
Serum FSH ⁹	X											
HbA1c	X									X	X	
Hepatitis B/C/HIV	X											
Safety labs (inc. urinalysis)	X	X ¹⁰	X	X		X		X		X ¹¹	X	X ¹¹
Blood sample for bone and calcium markers		X				X				X	X	
Pregnancy Test (WOCBP only) ¹²	X	X		X	X	X	X		X	X	X	X
Blood sample for genotyping ¹³	X											
Population PK blood sample ¹⁴		X	X	X		X		X		X	X	
Urine drugs of abuse	X	X				X				X	X	
Urine NTX		X				X				X	X	

Time and Events Table	Screening	Baseline ^{1, 2} (Day 1)	Week 2 ³ (Day 14)	Week 4 ³ (Day 28)	Week 8 (Day 56)	Week 12 ^{2, 4} (Day 84)	Week 16 (Day 112)	Week 18 ³ (Day 126)	Week 20 (Day 140)	Week 24 ^{2, 4} (Day 168).	Early Term ^{n-2, 5}	Follow Up ³ (21-28 days post last dose)
Sites to provide appropriate snacks and lunch	X	X				X				X	X	
Pedometer eDiary data collection (inc. review)	X	X ¹⁵		X		X		X		X		
MFIS / PGIS (muscle symptoms), PGIS (fatigue symptoms) and PROMIS – Short form FACIT fatigue 13a	X	X		X		X		X		X	X	
SF-36 / BPI and WPAI:SHP		X		X		X		X		X	X	
PGIC (muscle symptoms) and PGIC (fatigue symptoms)										X	X	
12 Minute Walk Test	X ¹⁶	X				X				X	X	
30STS		X				X				X	X	
IMP Capsule Counts			X	X		X		X		X	X	
Eye examination	X ¹⁷					X				X	X	
Wrist radiograph	X ¹⁸											
Concomitant medication review	X-----X											

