8.1.3 Analysis Populations

Screened Set	All subjects who sign the informed consent form.
Randomized Set	All subjects who are randomized.
Full Analysis Set (FAS)	All randomized subjects who receive at least one dose of study treatment.
Modified Analysis Set	All randomized subjects who receive at least one dose of study treatment and at least one on-treatment measurement*.
Safety Set	All subjects who receive at least one dose of study treatment.
Per protocol (PP) Set	All subjects in the FAS who do not violate inclusion or exclusion criteria and/or deviate from the protocol, in a way that could influence their efficacy assessment. Subjects who walk more than 1000m in the Baseline 12MWT will also be excluded from the set.
PK Set	All subjects in the FAS who receive REN001 and have at least 1 evaluable post-dose PK measurement (even if this is <Level of Quantification (LOQ)).

* For the primary endpoint this will be 12MWD

The FAS will be used for reporting demographic and baseline characteristic data, and as the primary analysis population for efficacy. Subjects will be analyzed by planned treatment. The PP set will be used for sensitivity analyses of the primary and secondary endpoints.

All safety analyses will be based upon the Safety Set. Subjects will be analyzed by the treatment received.

After all the data have been verified/coded/entered into the database, a review will be performed. The purpose of this review will be to define the analysis populations. The review will also check the quality of the data, identify outliers, and make decisions on how to deal with any data issues (e.g., missing values, withdrawals, protocol

deviations). After the pre-analysis review, resolution of all issues and documentation of all decisions, the database will be locked.

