2.0 (12Apr2023)	
Updates following feedback from the United States Food and Drug Administration (FDA) (Reference: 5090787) and team review:
 
 • Sections 3.2.2, 3.2.5, 10.2 and 10.3: Secondary Endpoints and Exploratory Endpoints – following FDA advice the Patient-Reported Outcomes Measurement Information System (PROMIS) Short-Form Functional Assessment of Chronic Illness Therapy (FACIT) Fatigue 13a T-score has been promoted to a secondary endpoint and Modified Fatigue Impact Scale (MFIS; physical sub-scale score) and Patient Global Impression of Change (PGIC; muscle symptoms) have been moved to exploratory endpoints. • Section 3.2.5 Exploratory Endpoints - Added phenotypic description questions as exploratory endpoints and included new Sections 4.11 and 10.3.10 to describe the endpoints and analyses. • Section 4.2 PROMIS - Moved from Section 4.7 to Section 4.2. Updated text to state PROMIS T-score is a secondary endpoint. • Sections 4.7 and 10.3.5: Modified Fatigue Impact Scale – moved from Section 4.2 to Section 4.7. Changes made concerning the recall period used. Added percent changes from baseline endpoint for each sub-scale score and the total score. Updated text to state MFIS physical sub-scale is an exploratory endpoint. • Section 4.3 Patient Global Impression of Change – updated section to include both muscle and fatigue symptoms, as both are now exploratory endpoints. Original Section 4.11 for PGIC (fatigue symptoms) removed. • Section 4.5 and 10.3.2: Pedometer Step Count – clarified that the collection of this data is optional and only subjects who have at least one average step count for a visit will be analysed. Clarified the analysis window for Week 4 data. • Section 6.7 and 12.7 Eye Examination – updated the spherical equivalent worst change to a decrease from baseline and updated the corresponding summary presentation. Added a listing for subjects with a ≥ 0.75 diopter change during the study. • Section 7.4 Full Analysis Set – modified definition to exclude subjects who were randomized but subsequently discontinued from the study for failing eligibility criteria. • Section 7.6 Per Protocol Analysis Set – updated criteria. • Section 8.2 General Methods – updated the order of testing to account for the change to the secondary endpoints. Clarified that baseline

Version (Date)	Summary of Changes

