8.2. GENERAL METHODS

All statistical testing will be at the 5% level of significance (2-sided) and all point estimates for the comparison between treatment groups will be accompanied by 2-sided 95% confidence intervals. To preserve the Type 1 error a fixed sequence testing procedure will be adopted. Testing will be on the FAS. The order of testing for the primary and secondary endpoints will be:

1. Change from Baseline at Week 24 in distance walked during the 12MWT
2. Change from Baseline at Week 24 in the PROMIS T-score

Continuous variables will be summarized using the number of non-missing observations (n), mean, SD, median, minimum, and maximum. Categorical variables will be summarized using counts and percentages.

Unless otherwise specified, the estimated mean and median for a set of values should be displayed to 1 more decimal place than the original values, and SD should be displayed to 2 more decimal places than the original values. The minimum and maximum should be displayed to the same number of decimal places as the original values. Deviations from this convention may arise to take account of the relevance of the precision (e.g., the distance walked in the 12MWT is reported to the nearest cm, but there is no relevance in presenting the mean to the nearest mm). These deviations from convention will be documented in the relevant analysis sections below.

Percentages will be displayed with 1 decimal place; except percentages will not be presented when the count is zero and 100% will be presented as an integer. Unless stated otherwise, percentages of subjects will be based on the number of subjects with non-missing data in the analysis set used for the presentation.

Baseline will be taken as the last available non-missing assessment prior to study drug administration (Day 1). Although the time of completion is not collected for QoL questionnaires (MFIS, PGIS, PROMIS, SF-36, BPI or WPAI:SHP), any completed on Day 1 will be deemed suitable for baseline as the questionnaires are requested in the protocol to

be completed prior to dosing and, even if after dosing, there is no anticipated effect after a single dose.

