14. CHANGES FROM PLANNED ANALYSES SPECIFIED IN THE PROTOCOL

- The secondary endpoints have been updated following FDA advice. The PROMIS T-score has been promoted to a secondary endpoint and MFIS physical sub-scale score and PGIC (muscle symptoms) have been moved to exploratory endpoints. The order of testing of endpoints has also been updated to align with this change.
- As the PGIC is assessed at the end of study treatment (Week 24 or Early Termination) a while on treatment strategy was proposed in the protocol. However, with some subjects not completing their PGIC assessment until more than a week after their last dose of study medication the strategy has been changed. The primary analysis will include all recorded data, regardless of the duration between the subject's last dose of study medication and the assessment. Given some subjects will have been off treatment for more than 7 days before recording PGIC, this analysis will no longer be referred to as a 'while on treatment' strategy; instead, this is a 'treatment policy' strategy. Subjects with no PGIC assessment will be considered as missing unless the incidence of missing PGIC data exceeds 5%. If the incidence exceeds 5% a multiple imputation approach will be used. A 'while on treatment' strategy has also been included as a supplementary analysis, where only assessments within 7 days of the last dose of study treatment will be included.
- A responder endpoint has been defined for the PGIC muscle symptoms and PGIC fatigue symptoms in addition to the 7-point scale endpoints.
- Two additional exploratory endpoints based on the 12MWD have been defined to further support the primary analysis. The endpoints are the first and last 6-minute periods of the 12MWD and aim to investigate whether there is a difference in treatment effect in these two periods.
- The supplementary analysis for the primary endpoint using a while on treatment strategy has been updated to an ANCOVA following review comments from the FDA. The original while on treatment analysis proposed in the protocol is now referred to as a treatment period restricted analysis.
- Added the exploratory endpoint for the phenotypic description questions (exercise tolerance, gait stability and myopathy) which are asked at Baseline and Week 24.

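### SAP 7.4 drops dosed subjects later discontinued from the study for failing eligibility; Section 14 does not list the change, and no efficacy analysis keeps everyone randomized and dosed

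*SAP*

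**What the plan says.** Protocol 8.1.3 defines the FAS as "All randomized subjects who receive at least one dose of study treatment", and the synopsis agrees. It is the primary efficacy population, analysed by assigned treatment.

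SAP 7.4 keeps those two conditions and adds a third, that subjects "have not been subsequently discontinued from the study for failing eligibility criteria". SAP 8.2 says of the primary and secondary tests: "Testing will be on the FAS".

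The SAP change log for version 2.0 records the edit ("modified definition to exclude subjects who were randomized but subsequently discontinued from the study for failing eligibility criteria") among updates attributed jointly to FDA feedback and team review. It gives no reason for this item. Section 14, headed "CHANGES FROM PLANNED ANALYSES SPECIFIED IN THE PROTOCOL", has six entries, and none mentions the FAS.

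Two protocol sections govern how such a subject leaves. Section 3.6 opens with "Individual subjects may be discontinued from the study drug in the following circumstances". Its item 3 covers "the discovery after administration of the first dose of study medication that the subject failed to meet protocol entry criteria", with the further condition that staying on would pose an unacceptable risk or undermine the study's objectives. Section 6.9 says of subjects who stop drug that "they will be strongly encouraged to continue in the study for their Week 12 and Week 24 visits".

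**The concern.** Removing ineligible subjects after randomization is easiest to defend when the rule depends only on facts fixed before randomization and is applied to everyone alike. This clause does neither. It selects on being discontinued from the study, which follows dosing and involves judgement. Of two subjects with the same violation, the one who stays, even off drug, remains in the primary analysis and the one who leaves is removed.

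What is at stake is the randomized comparison behind both confirmatory tests. SAP 8.3.1 already has rules for study withdrawal, with blinded adjudication and separate handling of related and unrelated reasons. The clause takes this group out before those rules apply. It also sits poorly with the treatment-policy estimand in SAP 10.1.1, which counts subjects whether or not they continue treatment.

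**Working it through.** **Which set each analysis uses**

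- Confirmatory tests: FAS (SAP 8.2).
- Other efficacy analyses: FAS by default (SAP 10).
- Primary-endpoint sensitivity analyses: FAS (SAP 10.1.4).
- Supplementary analyses: FAS, modified FAS or per protocol set. The last two are defined as subsets of the FAS (SAP 7.5, 7.6).
- Randomized set: disposition only (SAP 7.2).
- Safety set: baseline and safety only (SAP 7.3).

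No efficacy analysis therefore reaches beyond the narrowed FAS.

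**The plan's own figure**

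Inputs from SAP 3.5: difference 60 m, SD 125 m, two-sided 5%, 90% power, 1:1 allocation. The normal approximation gives 92 per arm (184). Noncentral-t power is 89.9% at 92 per arm and 90.3% at 93, so the stated 186 is reproduced.

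**Effect on power**

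The number removed is not in the documents, so these counts are assumed. Starting from 200 dosed subjects, noncentral-t power is 92.2% with none removed, 91.7% with 4, 90.8% with 10 and 90.3% with 14. Power is not the issue.

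**Effect on the estimate, per removed subject**

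Take 100 per arm. The SE of the difference is 125 × √(2/100) = 17.7 m. One subject whose value differs by D from the arm mean moves that mean by D/100.

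1. *Withdrawal adjudicated unrelated to PMM or treatment.* SAP 8.3.1 imputes under missing at random within arm, so the expected shift is about 0 m. This is the likelier route for an eligibility failure.
2. *An Early Termination walk is used at Week 24.* The shift is 125/100 = 1.25 m per SD from the arm mean, and 1.25/17.7 = 0.07 SE. Under the SAP 8.4 windows such a walk enters the model only on Days 63–105 (43 days) or, within Days 2–168, on Days 147–168 (22 days). That is 65 of 167 days. On the other 102 (Days 2–62 and 106–146) it is not used. This describes the windows; it is not a probability, because discovery dates are not given.
3. *Withdrawal adjudicated related, with no usable Early Termination walk.* SAP 8.3.1 draws the change from a normal distribution centred on the worst change seen in the study, with the visit distance kept at or above 0 m. This was simulated 2,000 times per scenario with 93 per arm and a 60 m difference. Assumed, not in the documents: Week 12/24 correlation 0.6, placebo mean change 0 or +30 m, baseline SD 150 m, and the baseline means below.

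| Baseline mean | Mean imputed change, placebo change 0 | Mean imputed change, placebo change +30 m |
|---|---|---|
| 500 m | −290 m | −271 m |
| 650 m | −326 m | −302 m |
| 800 m | −341 m | −314 m |

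Shift = (arm mean − imputed mean)/100:

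- Active arm, lowest: (60 + 290)/100 = 3.5 m. Highest: (90 + 314)/100 = 4.0 m.
- Placebo arm, lowest: (0 + 290)/100 = 2.9 m. Highest: (30 + 314)/100 = 3.4 m.

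In SE units, 2.9/17.7 = 0.16 and 4.0/17.7 = 0.23. In this case, removing an active subject raises the estimated difference and removing a placebo subject lowers it.

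**The case against.** The best defence has four parts.

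- *The removal is not arbitrary.* Protocol 3.6 item 3 carries the risk-or-objectives condition, and Section 3.6 limits the encouragement to stay to cases where it is appropriate. Two subjects with the same violation may therefore differ in a relevant way, and Figure 3, which sets out the process, is not shown in the text reviewed. This stands as a description, but the condition is itself judged after dosing, so it does not make membership a pre-randomization matter.
- *The removals will be visible.* SAP 9.1 tabulates the number in each analysis set, SAP 9.2 shows baseline data for both the safety set and the FAS, and SAP 8.2 lists all data for dosed subjects. A reader would see how many were removed and from which arm. That stands too. What is missing is an efficacy estimate with them included.
- *The change is disclosed.* SAP 2 asks only that changes from the protocol be identified in the SAP, and the change log does so. Nothing is concealed. But the log compares SAP versions, gives no reason for this item, and does not present it as a departure from the protocol. Section 14 exists for that purpose.
- *Bias is unlikely.* The sponsor and sites are blinded (Protocol 5.3, SAP 13), the screening committee confirms eligibility before randomization (Protocol 4), populations are settled before lock (Protocol 8.1.3), and unblinding follows lock (SAP 2). These safeguards lower the risk materially. They do not supply the missing analysis.

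**Conclusion.** The concern holds in all three parts: the FAS is narrower than the protocol's, Section 14 omits the change, and no efficacy analysis covers all randomized, dosed subjects. It should be corrected, on the strength of the text and not of a demonstrated bias. The count may be zero; SAP 9.2 itself allows for the safety set and FAS coinciding. The likeliest shift per removed subject is about 0 m. The range of 2.9 to 4.0 m needs both a related adjudication and the assumed inputs, and is an upper case. The direction of any net effect depends on which arm loses subjects.

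**What to change.** Restore the protocol definition in SAP 7.4 (all randomized subjects with at least one dose, analysed as randomized) for the primary and secondary tests. Handle these subjects under SAP 8.3.1 and keep the restricted set as a supplementary analysis. The per protocol set already excludes eligibility violators whose violation may affect efficacy, so the FAS clause is not needed for that purpose.

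At minimum, add a sensitivity analysis of both endpoints on all randomized, dosed subjects, and enter the FAS change with its reason in Section 14.

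The full fix costs one clause and one supplementary analysis. The minimum costs one sensitivity analysis and one Section 14 entry. Restored subjects may bring some imputed values into the primary analysis. If nobody is affected, the results do not change. Either change should be made before database lock.
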